### **Objectives:**

1. To compare the rate of IDH when intradialytic exercise is performed in the first half of the HD session as compared with that when intradialytic exercise is performed in the second half of HD.
2. To compare the prevalence of hemodialysis related symptoms when intradialytic exercise is performed in the first half of the HD session as compared with symptom prevalence when exercise is performed in the second half of HD.

3. To compare recovery time post HD when intradialytic exercise is performed in the first half of the HD session as compared with recovery time post HD when exercise is performed in the second half of HD.

**Study Design:** Multi-centre randomized crossover study comparing the rate of IDH over a 2-week period in 90 individuals on chronic HD when intradialytic cycling is performed in the first half of HD as compared with the rate of IDH when intradialytic cycling is performed in the second half of HD for 2 weeks.

**Population/Setting:** Adults with end-stage renal disease on chronic (>3 months) in-centre HD who are already participating in the Northern Alberta Renal Program (University of Alberta Hospital, Grey Nuns Hospital, Edmonton General Hospital, and St. Paul's Dialysis Unit); Southern Alberta Renal Program (Sheldon Chumir Hemodialysis Unit, South Calgary Hemodialysis Unit, Peter Lougheed Centre, North East Dialysis Centre, Northland Dialysis Centre); or the Manitoba Renal Program (Sherbrook Centre Dialysis Unit, Central Dialysis Unit and Seven Oaks Hemodialysis Unit) clinical intradialytic cycling programs are eligible to participate. Participants will act as their own comparisons.

*Inclusion criteria:* adult ( $\geq 18$  years old); receiving three times per week intermittent hemodialysis sessions; able to communicate in English; able to provide informed consent

*Exclusion criteria:* dialysis frequency not three times per week

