**BP Measurement:**

We will use the initial BP measurement obtained once the patient has commenced HD (i.e. patient “hooked up” and blood present in both venous and arterial lines) for the *baseline BP*. Blood pressure will be measured as per routine procedures used in the participants’ HD units (usual arm/leg, usual BP cuff). Pre and post HD BP will be collected as per usual HD Unit practice. During HD, BP will be collected more frequently than the usual HD routine (q30 min) at q15min intervals or more frequently when clinically indicated based on patient symptoms or status. This timing will be pre-programmed into HD machines to minimize work for bedside HD nurses. However, bedside HD nurses will need to record each BP measurement on the HD run sheet. Research assistant and/or clinical exercise program kinesiologist will be present at each cycling session to ensure outcome data is being collected.

**Primary Outcome:** *Difference in rate of intradialytic hypotension* between the 2 study time periods (early and late intradialytic exercise). Rate of IDH will be reported as episodes of intradialytic hypotension per 100 hours of HD. Intradialytic hypotension will be defined as the composite of >20 mmHg drop from baseline BP OR a drop in systolic BP to <90 mmHg during HD. A >20 mmHg reduction in blood pressure is justified as this magnitude of reduction from baseline BP has been associated with occurrence of HD-induced cardiac injury. In addition, a nadir BP of <90mmHg is the only definition of IDH associated with increased risk of mortality.

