### **Data Collection and Management:**

Baseline demographic and clinical data will be collected from the hemodialysis chart. This will include age, sex, race, time on hemodialysis, hemodialysis access, dialysis vintage, comorbidities (including hypertension, diabetes, congestive heart failure and ischemic heart disease), amount of fluid removed at each HD, hemoglobin, Kt/V (dialysis efficacy), medications and blood work results as measured on last monthly bloodwork. Each patient will be assigned a unique study identifier. Routine hemodialysis run sheets on which all BP measurements during HD are recorded will be copied after each treatment (with all identifying information removed) and labeled with only the patients’ unique study identifier. The patient's identifying information with the coded study numbers will be stored in a hardcopy file in a locked filing cabinet. In addition, this information will also be stored in a password protected electronic file on a secure research server located at the University of Manitoba, Rady Faculty of Health Sciences, Max Rady College of Medicine that is accessible only to required study staff. Local research staff at each study site will enter de-identified study data from hard copy data collection sheets into a dataset that is housed on the secure research server. All electronic data files will be password protected. Datasets from Calgary and Edmonton will be password protected, combined together and analyzed in Winnipeg. Participant study questionnaires (completed as hard copies) will have no identifying information other than the unique study number. All hard copies will be stored in a locked filing cabinet in the primary investigator’s office at each site. Both electronic and hard copy data will be destroyed after a period of 10 years.

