### **Data analysis:**

Demographic and baseline clinical data will be analyzed using the appropriate descriptive statistics and presented as mean (standard deviation), median (interquartile range), and proportion for parametric, non-parametric and categorical data, respectively. Linear mixed models will be used to analyze the associations between timing of exercise (first half or second half of HD) and intradialytic hypotension while accounting for duration of exercise, UF rate and

within patient data. Mean symptom burden score will be stratified by timing of intradialytic exercise and compared using paired Student's t-test. Similar analysis will be performed for time for recovery post HD.

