**Sample Size Estimation:**

We consider a 20% increase in IDH rate with intradialytic exercise in the second half of HD to be clinically significant and unacceptable. A previous study of 42 HD patients who exercised in the first half of HD observed IDH rate was 130 episodes per 100 hours of HD.

Assuming a standard deviation of 50, a sample size of 75 individuals (approximately 2250 hours of HD) will give us 80% power to observe a 20% increase in IDH rate with one-sided alpha 0.05. To account for study dropout, we will recruit a total of 90 individuals in total at the 3 sites (30 from each site Winnipeg, Calgary, Edmonton).

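### The primary IDH model leaves out each session's starting BP, so the late-early contrast carries avoidable noise: a loss of precision of uncertain size, not a bias

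*Protocol*

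**What the plan says.** Protocol, Data analysis, names the model: "Linear mixed models will be used to analyze the associations between timing of exercise (first half or second half of HD) and intradialytic hypotension". The same sentence then gives the adjustment, which is made "while accounting for duration of exercise, UF rate and" for the clustering of sessions by patient. Those are all the adjustment terms named.

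Protocol, BP Measurement, defines the reference value: "We will use the initial BP measurement obtained once the patient has commenced HD". The Primary Outcome paragraph defines an event as the "composite of >20 mmHg drop from baseline BP OR a drop in systolic BP to <90 mmHg during HD". The starting reading is therefore one side of every comparison in the first limb.

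Protocol, Data Collection and Management, shows that the value will be held for each session: "Routine hemodialysis run sheets on which all BP measurements during HD are recorded will be copied after each treatment".

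Protocol, Population/Setting: "Participants will act as their own comparisons". Under Intervention, each participant has six sessions per timing in two-week blocks, with no washout because carry-over is judged implausible. Sample Size Estimation sets the difference of interest: "We consider a 20% increase in IDH rate with intradialytic exercise in the second half of HD to be clinically significant and unacceptable".

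**The concern.** An unusually high first reading turns many later readings of that session into falls of more than 20 mmHg, and an unusually low one suppresses them. All readings of the session share this error, and it carries no information about exercise timing. The patient effect removes stable differences between patients but not swings from one session to the next. With six sessions per period, those swings do not average out fully.

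The model adjusts for exercise duration, which is realised only after timing is assigned, yet omits a reading that precedes the session's cycling and forms part of the event definition.

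At stake is the width of the interval around the late-early difference. The protocol calls a 20% increase unacceptable and expects no significant difference, so the conclusion will rest on how far the upper limit lies below 20%.

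**Working it through.** **1. The plan's own sample size.** Inputs from Sample Size Estimation: reference rate 130 per 100 h, 20% increase, SD 50, one-sided alpha 0.05, power 80%, n = 75. The difference is 0.20 × 130 = 26 per 100 h, and z = 1.645 + 0.842 = 2.487.

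- SD 50 as the SD of the paired difference: n = (50 × 2.487 / 26)² = 22.9, so 23.
- SD 50 per period, no correlation credited (SD of the difference 50√2 = 70.7): n = 2 × 22.9 = 45.7, so 46.
- Neither gives 75. That would need an SD of the difference of 26 × √75 / 2.487 = 90.6.
- Power at n = 75: Φ(26 / (70.7/√75) − 1.645) = Φ(1.54) = 93.8%, or 99.8% with an SD of the difference of 50.

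The stated 75 is not reproduced, but on the plan's inputs a crossover of 75 has more than 80% power. The omitted covariate therefore cannot be said to leave the trial short.

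**2. How the starting reading enters.** For patient i and session s, let the starting SBP be B = μ + u_i + e_is. Let a later reading at fraction t of the session be μ + u_i + p·e_is − D_is·t + noise, where p is the share of the starting deviation that persists through HD.

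- First limb: B minus the later reading = (1 − p)·e_is + D_is·t − noise. A high start raises the count with weight (1 − p). Measurement error in the starting reading adds in full, whatever p is.
- Second limb (<90 mmHg): a high start lowers the count with weight p.

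The two limbs pull in opposite directions, and u_i cancels in the first limb. What can be gained depends on p, on noise in the starting reading, and on how close patients run to 90 mmHg. The documents give none of these.

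**3. Gain by correlation.** If r is the within-patient correlation between starting SBP and session rate, the residual variance is multiplied by (1 − r²).

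| r (assumed) | 0.1 | 0.2 | 0.3 | 0.4 | 0.5 |
|---|---|---|---|---|---|
| variance factor | 0.99 | 0.96 | 0.91 | 0.84 | 0.75 |
| n = 46 becomes | 46 | 44 | 42 | 39 | 35 |
| n = 75 becomes | 75 | 72 | 69 | 63 | 57 |

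**4. Simulation of the composite.** Assumptions: 75 patients, 12 sessions, 16 readings over 4 h, patient effect removed, every low reading counted. SDs in mmHg: between patients 15, between sessions 12, reading noise 8. Mean fall by session end 15, with SD 8 between patients and 8 between sessions. No separate noise on the starting reading. The SE ratio is the square root of the adjusted/unadjusted variance ratio.

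| Mean start | p = 0.9 | p = 0.7 | p = 0.4 | p = 0 |
|---|---|---|---|---|
| 115 | √0.777 = 0.88 | √0.944 = 0.97 | √0.936 = 0.97 | √0.564 = 0.75 |
| 140 | √0.999 = 1.00 | √0.882 = 0.94 | √0.590 = 0.77 | √0.380 = 0.62 |
| 150 | √0.987 = 0.99 | √0.831 = 0.91 | √0.548 = 0.74 | √0.368 = 0.61 |

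At mean 115, r runs from −0.47 (p = 0.9) to +0.66 (p = 0), so the sign changes as the <90 limb takes over. At mean 140 and p = 0.9, r is 0.03 and the gain is nil.

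A second set of assumptions (session SD 10, reading noise 8, mean fall 20; p = 0.4/0.7/0.9/1.0) gave:

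- mean start 140 to 150, readings counted: about 0.64/0.75/0.86/0.89;
- mean start 120, readings counted: 0.87/0.92/0.99/0.99;
- onsets counted: 0.85 to 0.97 throughout.

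A further set of runs gave SE ratios of 0.60 to 1.01 for readings and 0.76 to 1.00 for onsets.

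**5. On the scale of the 26-per-100-h difference.** With an SD of the difference of 70.7, SE = 70.7/√75 = 8.16 and the one-sided 95% limit lies 1.645 × 8.16 = 13.4 per 100 h above the estimate. At an SE ratio of 0.60 this becomes 8.1; at 1.00 it stays 13.4. This illustration treats all of that SD as session-level noise. Any patient-by-timing variation would reduce the gain.

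**The case against.** The strongest case against is that this is an optional refinement. A mixed model's full covariate list is often left to a statistical analysis plan, which is not at hand and might extend it. In a randomised crossover, omitting a prognostic covariate does not bias the timing effect, and chance imbalance in starting BP is already covered by the standard error. The patient term absorbs much of the BP variation. The composite's second limb works against the first, so a single linear term may gain little.

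Most of this stands as a limit on the size of the point. It does not remove the point, because the protocol names its covariates. Adding a reading that is already collected and enters the event definition is a concrete change to a stated model. In the simulations precision never materially worsened.

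One technical objection also stands. Timing is assigned in blocks of six sessions, so from the second session of a block the starting reading follows earlier sessions under the same timing. It precedes that session's cycling but is not pre-treatment for the block. Treating it as unaffected relies on the protocol's no-carry-over premise.

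A reader might infer that the starting reading largely decides whether the first limb is met. No figure in the documents supports that: later readings and persistence matter as well. Nor is a minimum gain guaranteed.

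**Conclusion.** The point holds as a matter of precision. The stated model omits a pre-cycling reading, held for every session, that enters the first limb of the primary outcome directly. Its session-to-session variation is left in the residual.

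The size rests wholly on assumed BP parameters. The SE reduction runs from about nil to about 40% if every low reading is counted, and to about 24% (ratio 0.76) if onsets are counted. It is near nil where starting deviations persist through HD or where the two limbs offset each other, notably at low mean BP with the <90 limb prominent. The upper end needs a higher mean BP and low persistence. These figures take the first limb as systolic, which its wording does not state.

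Two stronger readings are not supported. The timing estimate is not biased, because order is randomised. The trial is not shown to be underpowered, because the plan's own inputs give 93.8% to 99.8% power at n = 75 under crossover formulas. The SD of 50 is itself an assumption, however, so that surplus is not assured.

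**What to change.** Pre-specify session starting SBP as a covariate in the primary IDH model and in the model for secondary outcome 1, which uses the same reference reading.

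- Enter it as two terms: the patient's mean starting SBP, and the session's deviation from that mean. If the model is fitted to period totals, use the period mean of the deviations.
- Allow a non-linear term for the deviation, because the two limbs of the composite can pull in opposite directions.
- State that, for sessions after the first of each block, the adjustment relies on the no-carry-over premise under Intervention.
- Report the model without starting SBP as a sensitivity analysis.

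The cost is a few lines of analysis text and a few degrees of freedom out of about 75 × 12 = 900 sessions. No new data are needed. The choice should be fixed before outcome data are examined by timing, so that it cannot be read as post hoc.

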**Withdrawal of subjects:**

Patients may withdraw from the study at any time with or without giving a reason. If the reason is given, it will be recorded on the case report form and primary investigator will be notified of withdrawal.

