**Secondary Outcomes:**

1. Difference in rate of intradialytic hypotension (episodes of hypotension per 100 hours of HD) between the 2 study time periods (early and late dialytic exercise) as defined by a >20 mmHg drop from baseline BP AND associated with symptoms (abdominal discomfort, yawning, sighing, nausea, vomiting, muscle cramps, restlessness, dizziness or fainting, and anxiety) or requiring intervention. Although this definition is proposed by KDOQI, practically it is harder to capture for research purposes. Nonetheless, we will capture as a secondary outcome to ensure no difference in rate between two groups.
2. Difference in frequency and severity of dialysis related symptoms during the weeks that incorporate intradialytic cycling in the first part of the HD sessions as compared with symptoms when intradialytic cycling is performed during the second half of HD will be measured using the symptom burden score as measured by the Dialysis Symptom Index (DSI). The DSI (Appendix 1) is a 30-item self-administered questionnaire with low administrative burden that measures the presence (yes/no) and severity (5 point Likert-scale) of common symptoms in HD patients (cramping, nausea, dizziness, fatigue, chest pain, and shortness of breath) and has been shown to be reliable and valid. Participants will complete the DSI at time of consent and then weekly at the end of the

midweek HD session (on Wed for MWF HD shifts and on Thurs for TTS HD shifts) for the duration of the study (i.e. each participant will complete the DSI a total of 5 times over the study).

3. Difference in time for recovery post-dialysis when exercise is performed during first half of dialysis as compared with time for recovery post-dialysis when exercise is performed during the latter half of HD: at each study assessment, participants will be asked to answer the question “Approximately how much time does it take to recover from a dialysis session”. Answers will be recorded in minutes. Prolonged post-HD recovery time, defined as the answer to the question “How long does it take to recover from a dialysis session” has been identified as a troubling symptom complex and important outcome unique to individuals receiving HD.

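### The paired t-test fixed for symptom burden and recovery time drops every patient seen under only one timing, which would understate harm from late cycling if some patients leave because of it

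*Protocol*

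**What the plan says.** The Data analysis section of the protocol gives two kinds of method. For intradialytic hypotension (IDH): "Linear mixed models will be used to analyze the associations between timing of exercise" and hypotension. For the Dialysis Symptom Index (DSI), mean burden is to be "stratified by timing of intradialytic exercise and compared using paired Student's t-test". For the third outcome: "Similar analysis will be performed for time for recovery post HD".

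Three other sections bear on this:

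- Withdrawal of subjects: "Patients may withdraw from the study at any time with or without giving a reason". No further data collection after withdrawal is described.
- Sample Size Estimation: 75 individuals are required, and "To account for study dropout, we will recruit a total of 90 individuals in total at the 3 sites".
- Secondary Outcomes, item 2: "Participants will complete the DSI at time of consent and then weekly", five times in all, so two scores per timing plus one at consent. Item 3 asks about recovery time at each study assessment and does not say whether consent counts as one.

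Under Intervention, Group 1 cycles early for two weeks and then late; Group 2 does the reverse.

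**The concern.** A paired t-test needs a value under both timings. A Group 2 patient who leaves during the first two weeks has late scores on file but no early study-week score, and is excluded. A Group 1 patient who leaves in the first two weeks is excluded too. A Group 1 patient who leaves after one late score is kept. So if late cycling makes some people feel worse and they leave, the test discards recorded evidence of this from Group 2 and keeps it from Group 1.

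Objectives 2 and 3 ask whether timing changes symptoms and recovery. Losing patients who do badly on late cycling moves the contrast toward no difference, the unsafe direction when the question is whether late cycling is acceptable.

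This is a method the protocol fixes, not a detail left for an analysis plan. The same section already uses, for IDH, a class of model that can include patients with one period only.

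**Working it through.** **Dropout allowance.** Recruited 90, required 75: 1 - 75/90 = 16.7%, and 75/(1 - 1/6) = 90. The percentage is derived; the protocol states none. The 75 was set for the IDH rate and is taken as given. (It does not reproduce from its own inputs: with a difference of 0.20 × 130 = 26 and an SD of the difference of 50, (50 × (1.645 + 0.842)/26)² gives 23. That is a separate matter.)

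**Pairs lost.** 16.7% is an upper bound, because someone who leaves after the first score of the second period still forms a pair. With 15 leavers at random times, 78.7 pairs remained on average: (90 - 78.7)/90 = 12.6% lost. With all 15 leaving just after their first late score, 82.5 remained: 7.5/90 = 8.3% lost.

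**Bias, weekly scores.** The documents give no SD, correlation or target difference for DSI or recovery time, so all inputs here are assumptions: between-patient SD 1, weekly error SD 0.4-0.6, SD of the patient-specific late effect 0.3-0.8, 90 patients and 15 leavers. Symptom-driven leavers go after their first late score, according to its rise since consent. Shrinkage = 1 - paired estimate/true effect.

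| Leavers | True effect | Paired estimate | Shrinkage | Mixed model |
|---|---|---|---|---|
| All random | 0.20 | 0.197 | none beyond simulation error | 0.198 |
| 5 of 15 symptom-driven, effect SD 0.3 | 0.20 | 0.198 | 1% | - |
| 5 of 15, effect SD 0.5 | 0.20 | 0.186 | 7% | - |
| 5 of 15, effect SD 0.8 | 0.25 | 0.217-0.222 | 11-13% | - |
| All 15, little variation in effect | 0.20 | 0.191 | 5% | 0.203 |
| All 15, moderate variation | 0.20 | 0.172 | 14% | 0.204 |
| All 15, large variation, strong dependence | 0.25 | 0.175 | 30% | 0.251 |

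A separate repeat gave 0.19 (from 0.20) and 0.22 (from 0.25) with 5 of 15 symptom-driven, that is 5% and 12%. With all 15 it gave 0.16-0.19 (from 0.20) and 0.17 (from 0.25). The bias is 0.03-0.34 standard errors in the one-third rows and about 0.7 in the last row.

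**Bias, harsher set-up.** One score per period, SD 1, correlation 0.5 (SD of difference √(1 + 1 - 2 × 0.5) = 1), true effect 0.30, and every leaver losing the pair, so 75 pairs remain.

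- Random dropout: paired 0.30, maximum likelihood on all observed periods 0.30.
- All 15 leavers from Group 2, with high late scores: paired 0.20-0.23, likelihood 0.30.
- Leavers from both groups because late is worse than early, so that Group 1 leavers have no late score: paired 0.00-0.14, likelihood 0.06-0.18.
- True effect 0, Group 2 leavers as above: paired -0.06 to -0.11, likelihood about 0. The bias is thus a downward shift, which can also make late cycling look slightly better than it is.

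With 5% dropout the symptom-driven mechanisms give paired estimates of 0.21-0.28 against 0.30.

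**The case against.** A paired t-test is a standard choice for a two-period crossover, and missing-data handling is commonly left to an analysis plan that is not shown here. That explains silence on missing data. It does not alter the fact that the named test excludes one-timing patients by construction.

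The stronger objection concerns the mechanism. A reader might infer that a sixth of patients will be lost because late cycling makes them feel worse. The documents do not support that. The 15 are an all-cause allowance, no reasons for dropout are given, and the Intervention section and the cycling-programme description let participants skip cycling while staying in the study. Late cycling lasts two weeks, in people already used to cycling. This stands: symptom-driven exit is plausible but assumed, and having all 15 leave for that reason is an extreme case.

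A reader might also infer that a mixed model removes the problem. It stays within 0.01 of the truth only where leaving depends on recorded scores, and those runs treated the variance components as known. It cannot recover the late response of Group 1 patients who leave before any late score.

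Finally, the consent DSI is not clearly a neutral reference. The Manitoba programme description has participants already cycling in the first half, so consent probably reflects early cycling there. Collection at consent is explicit for the DSI only.

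**Conclusion.** The point holds, with modest and conditional consequences. What is certain is that the fixed test drops one-timing patients, that the plan expects withdrawals, and that lost pairs cannot exceed 15 of 90 if dropout is as allowed for. What is conditional is the bias. In the weekly-score simulations it is nil if dropout is random, about 5-12% shrinkage if a third of leavers are symptom-driven (nearer 1% if patients differ little in their response), and about 5-30% if all are. The harsher set-up gives more. These sizes rest on assumed variances and withdrawal mechanisms. The direction does not vary: every mechanism tried in which patients leave because late cycling is worse pulled the late-minus-early estimate down.

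The documents do not support saying that the secondary results will be biased, or that the primary IDH analysis is touched. The change is worth making because it is cheap and guards against an error in the unsafe direction.

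**What to change.** In Data analysis, replace the paired t-tests for DSI burden and recovery time with a linear mixed model on all weekly assessments from every randomised patient. Use fixed effects for assigned timing and period, and random patient and timing effects. State that patients with data under one timing only are included. Where a consent value is collected, use it as a pre-period score with its own mean, and note that it may reflect usual first-half cycling. State whether recovery time is asked at consent.

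Keep the paired t-test on patients with both timings as a sensitivity analysis, and report withdrawals by group and by the timing in force. That table would show whether Group 1 patients leave before any late score, the case the model only partly corrects.

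Cost: a few sentences, with no new patients or visits, because the weekly scores are already collected. The model relies on missingness depending on observed scores and is slightly less simple to report. With random dropout it costs nothing in power (71% against 70% for the paired test in the simulated case).
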